The appropriate personnel from the site and the Sponsor will assess whether study/investigational treatment should be discontinued for any participant whose treatment code has been broken inadvertently for any reason.

Participants who discontinue the investigational treatment should NOT automatically be considered withdrawn from the study unless they explicitly withdraw their consent. They are expected to continue attending study visits according to protocol assessments as planned in the assessment schedule (with exception of drug dispensing and drug administration). If they fail to return for these assessments for unknown reasons, every effort (e.g. telephone, e-mail, and letters) should be made to contact them as specified in [Section 5.6.4](#).

Missed or rescheduled visits or assessments should not lead to automatic discontinuation.

Assessments required upon discontinuation from treatment epoch are detailed in the “PPW” column in the assessment schedule ([Table 6-1](#)) should be completed and recorded in the eCRF. The investigator must determine the primary reason for the participant’s discontinuation of study treatment and record this information on the Dosage Administration eCRF.

Participants must be followed for 12 weeks after their last administration of investigational treatment (once it is determined as a permanent study drug discontinuation) or PPW visit performed at which time they will perform the Follow-up visit assessments (EoS).

The investigator must also contact the IRT to register the participant’s discontinuation from study treatment, and also register the visits with no treatment dispensed until PPW/TEC and EoS.

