5.6.3 Withdrawal of informed consent

Participants may voluntarily withdraw consent to participate in the study for any reason at any time. Withdrawal of consent occurs only when a participant:

- Does not want to participate in the study anymore
- and
- Does not allow further collection of personal data

In this situation, the investigator should make a reasonable effort (e.g. telephone, e-mail, letter) to understand the primary reason for the participant’s decision to withdraw his/her consent and record this information.

Study treatment must be discontinued and no further assessments conducted, and the data that would have been collected at subsequent visits will be considered missing.

Further attempts to contact the participant are not allowed unless safety findings require communicating or follow-up.

All efforts should be made to complete the assessments prior to study withdrawal. A final evaluation at the time of the participant’s study withdrawal should be made as detailed in the assessment [Table 6-1](#), PPW visit.

Novartis will continue to keep and use collected study information (including any data resulting from the analysis of a participant’s samples until their time of withdrawal) according to applicable law.

For US and Japan: All biological samples not yet analyzed at the time of withdrawal may still be used for further testing/analysis in accordance with the terms of this protocol and of the informed consent form.

For EU and RoW: All biological samples not yet analyzed at the time of withdrawal will no longer be used, unless permitted by applicable law. They will be stored according to applicable legal requirements.

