2.1 Data analysis general information

The statistical analysis will be performed by Novartis internal statisticians and programmers.

Unless otherwise stated, summary tables/listings/figures will be presented by treatment group in the respective analysis set. Tables showing only baseline data will also include a total column.

Categorical data will be summarized as frequencies and percentages. Percentages will be calculated as below:

- For population level summaries (like Demographic, AEs, Medical history...etc.), percentages will be calculated using number of participants in each reporting group as the denominator.
- For by visit summaries, percentages will be calculated using the number of participants in the analysis set with an assessment at the specified visit as the denominator.
- For specific event based summaries, the denominator will only include the subset of the analysis population of participants at risk at a specific point in time (Kaplan-Meier approach).

Continuous data will be summarized by presenting the number of non-missing observations, mean, standard deviation (SD), median, minimum and maximum, both for raw (absolute) values and for changes from baseline. Summary tables will be presented wherever applicable by visit if not otherwise specified.

Specified parameters of interest will be listed by treatment group, records will be ordered by country/center/participant and time of assessment.

General information on treatment group labels, decimal places and other output related information will be specified in the specification document for tables, figures and listing (TFLs) shells accompanying this analysis plan.

Statistical analysis will be performed using SAS[®] statistical software (SAS Institute, Cary, NC, USA.) version 9.4 or higher.

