For efficacy parameters: In case of competing assessments within a visit window, the assessment value closest to the scheduled visit day will be used. In case of equal distances, the earliest assessment value will be used. Visit window will not be applicable for TEC and EoS.

For safety parameters: In case of competing assessments within a visit window, the worst assessment value within the visit window will be used. This rule also applies for worsening in cognition as a safety measure.

Listings will include all assessments, sorted by date of assessment, flagging unscheduled visits. The listings will include analysis windows and corresponding flags to indicate the assessment's inclusion in the analysis.

Treatment Epoch Completion (TEC) and End of Study (EoS) and other points in time of interest

TEC is the end of treatment phase visit (i.e., visit 299) that will be completed for all participants after discontinuation of treatment. The same visit will also be completed in case of PPW. PPW is the premature study withdrawal.

EoS is a Follow-up visit scheduled after TEC/PPW, per urgent safety measure (USM) on 11-Jul-2019, and its follow-up letter dated 12-Dec-2019, Modified EoS visits can be scheduled anytime after receipt of this notification but no later than 15-Mar-2020. (i.e. the requirement from 11 July 2019 USM for the 6 month timeframe between modified TEC and mEoS visits is no longer required.).

Participants who were attending study visits (i.e., continuing in the study) but already off-treatment at time of USM were to come for EoS straight (no TEC required).

An assessment will be on treatment if it is before or at last day on study drug + 31 days. The last assessment before or at last day on study drug + 31 days will be referred to as "last on treatment" assessment. The last assessment after last day on study drug + 31 days will be referred to as "last off treatment" assessment. For deriving "last on treatment" or "last off treatment", last assessment date of RBANS will be used. That means, to derive the last on treatment and last off treatment for all the parameters, regardless of their actual assessment

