dates, RBANS last assessment date will be used as reference date. Note: the “last on treatment” and “last off treatment” flag will be created for each participant at visit level (not at the individual assessment level). If there is missing RBANS assessment at the specific visit, then date of the first day corresponding to that visit (i.e. non-missing assessment of that parameter under consideration) will be used to derive the “last on/off treatment” assessment.

Note: On treatment is a period from first dose to last dose + 31 days.

For example:

1. If a participant has the last dose on 13-Jul-2019, then “on treatment” period would span from first dose to 13-Jul-2019 + 31 days.
2. If a participant has the last dose on 09-Apr-2019, then “on treatment” period would span from first dose to 09-Apr-2019 + 31 days.

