2.4 Treatments (study treatment, rescue medication, concomitant therapies, compliance)

2.4.1 Study treatment / compliance

The duration of exposure to study drug is defined as the time (in days) from the first study drug administration to last study drug administration + 31 days.

The duration of exposure will be calculated as

(last dose date + 31 days) – first dose date + 1.

Duration of exposure to CNP520 will be summarized as continuous variable (in days) and categorical variable, using categories ≥ 1 day (any exposure), ≥ 3 months, ≥ 6 months, ≥ 1 year, ≥ 1.5 years.

For each treatment group, the participant-years will be calculated as

(sum of the durations of exposure for all participants in the group)/365.25) and will be summarized.

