2.8.1 Adverse events (AEs)

Treatment-emergent AEs (TEAEs) are events that either started after the first dose of study drug or events present prior to the start of study drug but increased in severity since the first dose. Adverse events reported within 31 days (5 half-lives) from study drug discontinuation date (i.e., last dose date) will be considered as TEAE. AEs reported more than 31 days after study drug discontinuation will not be considered treatment emergent (non-TEAE).

TEAEs and non-TEAEs will be summarized separately on the SAF.

Tables

TEAEs, SAEs, deaths and non-TEAEs will be summarized as follows

- TEAEs regardless of relationship to study drug by SOC, PT and maximum severity
- non-TEAEs, regardless of relationship to study drug by SOC and PT
- TEAEs causing study drug discontinuation by SOC, PT and maximum severity
- TEAEs related to study drug by SOC, PT and maximum severity
- TE-SAEs regardless of relationship to study drug by SOC and PT and maximum severity

Note: For missing information on AE relationship to study drug, the most conservative approach will be considered: If information on relationship of the AE to study drug is missing, the AE will be considered as related to study drug for reporting TEAEs.

The above summaries are generally without exposure adjustment, except from TEAEs by SOC and PT: this summary will be presented with exposure adjustment. The exposure-adjusted incidence rate of adverse events is defined as the number of participants with the adverse event divided by total participant years at risk in the treatment group. The time at risk for each participant will differ for each adverse event. For participants with events, only the time until the first event contributes to the total participant years at risk. For participants who do not experience the event, the time at risk will be calculated using the duration of exposure as defined in [Section 2.4.1](#). The exposure-adjusted incident rate will be summarized per 100 participant years. For participants with multiple occurrences of the same event, the event will be counted only once per participant.

Adverse events will be reported according to the latest MedDRA dictionary version available at the time of database lock.

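### Off-drug adverse events (non-TEAEs) are reported only as crude percentages of the whole safety set, so they refer to no stated period and are diluted by anyone without off-drug follow-up

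*SAP*

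**What the plan says.** SAP 2.8.1 classes an adverse event as non-treatment-emergent (non-TEAE) when it is reported more than 31 days after study drug stops. Non-TEAEs are summarised separately on the safety set (SAF) by SOC and PT. On exposure adjustment the section states: "The above summaries are generally without exposure adjustment, except from TEAEs by SOC and PT".

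SAP 2.1 names AEs among the population-level summaries, for which "percentages will be calculated using number of participants in each reporting group as the denominator". SAP 2.2 admits to the SAF everyone who received study medication; no off-drug observation is required.

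The only time at risk in the plan is the exposure duration in SAP 2.4.1, which runs "from the first study drug administration to last study drug administration + 31 days". It ends where the non-TEAE period begins.

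Protocol 7.1 collects AEs until end of study (EoS). When EoS falls depends on the participant:
- **After the urgent safety measure (USM) of 11-Jul-2019**, SAP 2.1.1 says "Modified EoS visits can be scheduled anytime after receipt of this notification but no later than 15-Mar-2020"; the notification is dated 12-Dec-2019.
- **Participants still attending but** "already off-treatment at time of USM were to come for EoS straight (no TEC required").
- **Earlier individual discontinuations**: protocol 5.6.2 sets 12 weeks from last dose "or PPW visit performed at which time they will perform the Follow-up visit assessments (EoS").
- **Withdrawal of consent**: protocol 5.6.3 says "Study treatment must be discontinued and no further assessments conducted".

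**The concern.** A participant with no observation after day 31 cannot contribute a non-TEAE but is still counted as event-free. A participant observed for 300 days and one observed for 50 carry the same weight. The resulting percentage is not an incidence over any period a reader could name.

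The SAP avoids this elsewhere. By-visit percentages use participants with an assessment, event-based summaries use participants at risk (both SAP 2.1), and TEAEs by SOC and PT receive an exposure-adjusted rate.

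The off-drug period matters here. The trial stopped because cognition worsened on active drug. The rationale for protocol Amendment 03 records that imbalances in body weight and brain volume were still seen after wash-out, and that cognitive testing and volumetric MRI were then dropped from the modified EoS visit. AEs were among the few assessments kept, so this table is one of the main tabulated outputs on late safety.

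**Working it through.** **The plan's own figure.** SAP 2.8.1 equates 31 days with five half-lives. Protocol 1.1 gives a half-life of about 150 hours: 5 × 150 / 24 = 31.25 days. It reproduces.

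**Possible off-drug observation.** Days = (EoS − last dose) − 31. The two last-dose dates below are worked examples in SAP 2.1.1 (for one of them: "If a participant has the last dose on 09-Apr-2019"). They are not a distribution of actual follow-up.

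| Case | EoS − last dose | Off-drug days |
|---|---|---|
| Consent withdrawn while on drug | – | 0 |
| EoS exactly 12 weeks after last dose | 84 | 53 |
| Last dose 13-Jul-2019, EoS 12-Dec-2019 | 152 | 121 |
| Last dose 13-Jul-2019, EoS 15-Mar-2020 | 246 | 215 |
| Last dose 09-Apr-2019, EoS 11-Jul-2019 | 93 | 62 |
| Last dose 09-Apr-2019, EoS 15-Mar-2020 | 341 | 310 |

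For the July case, the date of the EoS visit alone gives 215 / 121 = 1.8-fold.

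**Effect on a crude percentage.** The documents give no event rate, so constant rates are assumed. Percentage = 1 − exp(−rate × days / 365.25).

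| Assumed rate per participant-year | 53 days | 121 days | 215 days |
|---|---|---|---|
| 0.1 | 1.4% | 3.3% | 5.7% |
| 0.5 | 7.0% | 15.3% | 25.5% |
| 1.0 | 13.5% | 28.2% | 44.5% |

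**Between arms.** Assume equal true rates, 20% early stoppers in one arm against 10% in the other, and everyone else at (121 + 215) / 2 = 168 days. At 0.5 per year, 168 days gives 20.5%. If early stoppers have no off-drug time, the crude figures are 0.80 × 20.5 = 16.4% and 0.90 × 20.5 = 18.5%, a ratio of 0.80 / 0.90 = 0.89. Among participants actually followed, both arms show 20.5%.

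Over rates 0.1 to 1.0, the crude ratio is 0.93 to 0.94 if early stoppers have 53 or 62 days, and 1.05 to 1.08 at 310 days. The person-time rate ratio is 1.00 throughout, because the hazard was assumed constant.

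**When the hazard is not constant.** Same set-up, with the hazard (equal in both arms) changing at off-drug day 60:

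| Hazard per year before, after day 60 | Early stoppers' off-drug days | Crude ratio | Rate ratio |
|---|---|---|---|
| 1.0, 0.5 or 0.5, 1.0 | 0, 53, 62, 310 | 0.889 to 1.066 | 0.982 to 1.020 |
| 1.0, 0.1 | 53 | 0.976 | 1.050 |
| 1.0, 0.1 | 62 | 0.986 | 1.054 |
| 1.0, 0.1 | 310 | 1.018 | 0.948 |

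With a two-fold change the rate ratio stays within 0.02 of 1.00. With a ten-fold fall the crude ratio is the closer of the two in all three cases shown, although with no off-drug time for early stoppers it remains 0.889.

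**The case against.** The strongest reply is that this is a disclosed choice. The SAP says AE summaries are mostly unadjusted and names its exception. The study ended early, the report is abbreviated, safety is descriptive, and no test or decision rests on this table. SAP 2.3.1 reports discontinuation with reasons and missing EoS assessments, SAP 2.8.1 lists every AE, SAP 2.8.2 covers deaths, and weight, cognition and brain volume have their own off-treatment summaries. The table shells are not in the documents and might add more. All of that stands and keeps the point minor. None of these outputs, as specified, gives a non-TEAE frequency among participants who were observed off drug.

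Three stronger readings are tempting, and the documents do not support them.
- **That the comparison between arms is biased.** Arms were randomised and blinded, and all participants on drug were told to stop by the same notification, so off-drug windows should be similar. Nothing in the documents shows arm differences in early stopping; the 10% against 20% above is invented.
- **That dilution can be sized from the planned drop-out of about 6.9% a year (protocol 9.8).** That figure is planned overall drop-out, not the share withdrawing consent on drug. Protocol 5.6.2 expects those who stop drug to keep attending and then have a follow-up visit, so many would contribute off-drug time.
- **That a rate per participant-year is always better.** The ten-fold case above shows otherwise, and a transient effect after stopping is plausible, since the cognitive worsening reversed after wash-out.

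**Conclusion.** The point holds, as minor. As specified, the non-TEAE percentages refer to no stated period and count participants without off-drug follow-up as event-free. This follows from the text alone and needs no assumption about rates or arms. How far the percentages are diluted cannot be estimated from the documents. The percentages and ratios computed here illustrate possible size only; event rates, early-stopper shares and the day-60 change are assumptions, and the 62- and 310-day windows are the extremes of one worked example. Distortion between arms is possible only if early stopping or withdrawal differed by arm, and is probably modest.

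**What to change.** In SAP 2.8.1, keep the SAF table and add for each arm:
- the number of participants followed beyond last dose + 31 days;
- the percentage with a non-TEAE among them, by SOC and PT;
- the total off-treatment participant-years.

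These need no hazard assumption. The first two remove the dilution and the third shows how much observation lies behind the percentage. Then give the rate per 100 off-treatment participant-years as a descriptive figure, noting that it assumes a roughly constant off-drug hazard.

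Define time at risk from day 32 after last dose to the first event, or to EoS or last contact. Protocol 7.2.2 requires all SAEs to be reported until 30 days after EoS or PPW, so events can arrive after that end date. Either count only events up to it, or extend the window for SAEs by those 30 days.

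The cost is one extra table and one new time-at-risk definition, both from dates and AEs already collected. The downside is that the rate can be further from the truth than the crude percentage if the off-drug hazard changes sharply, which is why it should supplement the crude table and not replace it.

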2.8.1.1 Adverse events of special interest / grouping of AEs

An adverse event of special interest (AESI) is a set of adverse events that are of scientific and medical concern specific to a compound. These groupings are defined using MedDRA terms, SMQs (standardized MedDRA queries), HLGs (high level group terms), HLT (high level terms) and PTs (preferred terms).

Customized SMQs (Novartis MedDRA queries, NMQ) may also be used. An NMQ is a customized group of search terms which defines a medical concept for which there is no official SMQ available or the available SMQ does not completely fit the need. It may include a combination of single terms and/or an existing SMQ, narrow or broad.

AESIs as specified in the CNP520-specific Development Safety Profiling Plan (DSPP) are grouped in the corresponding Case Retrieval Sheet (eCRS) and analysed as a specific group along with other risk search terms.

The search criteria for each of the risks and events will be based on MedDRA and will be comprised by the eCRS. The most recent eCRS at the time of database lock will be used to determine the MedDRA search criteria for identification of the adverse events of special interests.

Tables

Number and percentages of participants with treatment emergent adverse events of special interest by risk and MedDRA levels will be summarized on SAF.

2.8.2 Deaths

Tables

Deaths regardless of relationship to study drug by SOC and PT will be summarized on the SAF.

Listings

Deaths will also be listed separately.

2.8.3 Laboratory data

Tables

Number and percentages of participants with newly occurring or worsening laboratory abnormalities meeting the clinically notable criteria at any time post-baseline visit will be summarized for all parameters as specified in [Appendix 5.6](#) of this document.

For a participant to meet the criterion of a newly occurring clinically notable value, the participant needs to have a baseline value that is not clinically notable for that parameter. For a participant to meet the criterion of a worsening clinically notable value, the participant needs to have a baseline value that is clinically notable and also have a worse post-baseline value. For participants with missing baseline value, any post-baseline notable value will be considered as newly occurring.

For each participant, all available post-baseline laboratory tests will be used to compare with the notable criteria. If at least one of the results, for a particular parameter, exceeds the criteria, the value will be considered as clinically notable abnormal for that parameter. A participant can be counted in both, low and high categories.

The upper limit of normal (ULN) for each parameter is available in the lab dataset. All available post-baseline laboratory tests will be used to compare with the criteria specified in [Appendix 5.6](#). If at least one of the results, for a particular parameter, exceeds the criteria, the value will be considered as notable abnormal for that parameter. To categorize the abnormality, use the worst case within a lab parameter for a participant if multiple abnormality occurrences exist for the same lab parameter.

The laboratory parameters will be reported in SI units.

The number and percentage of participants with newly occurring or worsening liver enzyme abnormalities meeting the clinically notable criteria at any time post-baseline visit as specified in [Appendix 5.3](#) will be summarized.

Figures

Box-plots for lab parameters of hematology, biochemistry and urinalysis over time by treatment group will be provided:

2.8.4 Other safety data

2.8.4.1 ECG and cardiac imaging data

12-lead ECGs will be performed at screening and throughout the study in supine position. The ECG values will be interpreted and analyzed centrally. The QT intervals will be corrected according to the formula by Fridericia:

Fridericia's formula: $QTcF = QT/RR^{1/3}$

Tables

The number and percentage of participants with newly occurring or worsening clinically notable ECG abnormalities at any time post-baseline visit will be summarized for all parameters as specified in [Appendix 5.6](#).

Figures

Box plots over time will be presented by ECG parameter and treatment group.

